2.7 Feasibility

The HVTN 805/HPTN 093 team has the significant advantage of data and experience from the AMP Study to inform an assessment of the feasibility of HVTN 805/HPTN 093, appreciating that while this concept is significantly different from the parent AMP Study, all participants for HVTN 805/HPTN 093 will be from the AMP cohort at sites and in communities now familiar to the AMP and HVTN 805/HPTN 093 teams. AMP accrual and retention rates, early termination rates, data quality and safety have been excellent by any standard, perhaps particularly so considering the demanding nature of the 2 AMP trials (HVTN 704/HPTN 085 and HVTN 703/HPTN 081) that, together, enrolled 4,625 participants for 2 years of monthly clinic visits and q8-weekly IV infusions (111, 112). In over 35,000 IV infusions administered to date, no procedural complications (eg, local IV site infection,) have been observed; 2/3 of participants receive VRC01 and very low rates of infusion reactions have been observed, all of which have been medically managed exceptionally well (111, 113).

While overall performance in AMP has been exceptional, the HVTN 805/HPTN 093 team also considered site-specific performance and other considerations in determining which sites will implement HVTN 805/HPTN 093. Considerations include: site-specific retention performance; timeliness and accuracy of safety data submission; access to potentially eligible participants; site capacity for frequent clinic visits and close clinical monitoring of participants; access to and capacity for close partnership with primary HIV care, including timely ART re-initiation; and site willingness to participate, including receptivity of site investigators, community representatives, and regulatory authorities.

Partnership with regional investigator, regulatory, and community representatives for the development of HVTN 805/HPTN 093 has already begun in earnest and is ongoing.

A symposium with sub-Saharan African investigators, regulatory and public health representatives, and community representatives, including representatives from local Community Advisory Boards (CABs), was held in August 2019 in Cape Town, South Africa, with co-sponsorship by the South African Medical

Research Council (SAMRC). Attendees were engaged and were supportive of contributing to the global HIV cure and remission research agenda, including with rigorously-designed ATIs like HVTN 805/HPTN 093, with some participants stating, *“We need this,” “This is for our communities,”* and *“This [an AMP ATI] is a first step.”* Understanding and engagement was also evident in attendee questions and dialogue throughout the consultation.

Early in development in early 2019, the HVTN 805/HPTN 093 team also solicited and received input and support from sub-Saharan African AMP investigators, policy makers, basic and clinical scientists, and from the AMP Community Working Group (AMP CWG), whose members include community educators, recruiters, and CAB members from each AMP site. Several forums throughout 2019 also provided opportunities for additional discussion and feedback regarding HVTN 805/HPTN 093 with AMP Protocol Team and site representatives (eg, investigators, clinic coordinators) and AMP CWG members.

Community engagement and site readiness, as described above, are necessary but not sufficient to support the conduct of HVTN 805/HPTN 093. AMP participant willingness to participate in the ATI is a crucial additional feasibility consideration. Again, interim data from AMP provides some insight here.

A mixed-methods AMP sub-study enrolled 300 participants—50 AMP participants from each of 6 sites based throughout the US. Upon exiting the AMP Study, each participant took part in a brief survey and a 60-minute interview regarding their demographics, understanding of bnAbs, and any enrollment or retention barriers and facilitators they experienced. In an interim analysis, about a quarter of participants expressed concerns about the AMP Study time commitment or the experimental nature of the VRC01 product and the associated uncertainty regarding its efficacy. All participants expressed a strong sense of appreciation for and positive identification with their clinical research site. For example, one participant noted: *“I’m going to volunteer for clinical research, especially if it’s research that’s going to affect the community that I’m part of”* and another enthused *“I’m such a big fan of [the CRS] that any research study that they pretty much put forward, I’m like interested in, or definitely highly support.”* Several participants cited the additional medical care they received at the clinic as a facilitator of ongoing study participation: *“[staff member name] took on this role of like a secondary primary care physician for me. In addition to the care I was getting at my doctor’s office, I also felt like I was getting another set of eyes on me. I just felt cared for.”* Another observed *“I liked how I got tested so often, and they were there to help me with any concerns I had, whether in regard to the infusion or to getting tested for other STDs or STIs.”*

While the scope of the sub-study is limited to the US, anecdotal evidence from sites around the world, coupled with the exceptional accrual and retention observed in the AMP studies to date (112), suggests that the experience participants have with their HVTN and HPTN AMP sites, globally, is a strongly positive motivator for continued engagement with their site. Furthermore, many

sites retain engagement with their participants through various means even post-AMP and have the ability, prespecified in site-specific AMP consent forms approved by their Institutional Review Boards/Ethics Committees (IRBs/ECs), to reach out to participants after they've exited the trial to inquire about their interest in possible future research.

Thus, HVTN 805/HPTN 093 as described herein is thought to be feasible thanks in large part to the selection of sites for AMP and their conduct of the study, including their relationships with site participants and their community and regulatory partners.

2.8 Conclusion

The AMP ATI is uniquely positioned to test for ART-free virologic control and to enhance understanding of the immunologic (ie, host) and virologic mechanisms and biomarkers of control among individuals who acquired HIV in the presence of circulating bnAb. Here, we have an opportunity to translate the intriguing preclinical observations in SHIV-infected primates (53) to humans. This trial will extend early clinical observations, explore potential mechanisms, validate biomarkers of control, and discern whether AMP participants who became HIV-infected while on trial may become “post-bnAb controllers,” capable of early ART- and/or bnAb-induced immunologic responses that change the course of their infection.

3 Study design

3.1 Hypotheses

3.1.1 Primary hypotheses

- Individuals who initiated ART early in HIV infection in HVTN 703/HPTN 081 will suppress plasma viremia and maintain CD4+ T-cell counts longer during ATI than historical cohorts (ie, SPARTAC African and non-African cohorts described in Gossez et al (1) comprising individuals who initiated ART early in HIV infection without other interventions).
- Individuals who initiated ART early in HIV infection and also received VRC01 within 8 weeks before or after acquiring HIV in HVTN 703/HPTN 081 will suppress plasma viremia and maintain CD4+ T-cell counts longer during ATI than those who initiated ART early in HIV infection and received placebo within 8 weeks before or after acquiring HIV in HVTN 703/HPTN 081.
- ATI will be safe and well-tolerated in individuals who acquired HIV during their participation in HVTN 703/HPTN 081.

3.1.2 Secondary hypotheses

- Individuals who initiated ART early in HIV infection and also received VRC01 within 8 weeks before or after acquiring HIV in HVTN 703/HPTN 081 will have enhanced cellular and humoral responses compared with those who initiated ART early in HIV infection and received placebo within 8 weeks of acquiring HIV in HVTN 703/HPTN 081.
- Individuals who initiated ART early in HIV infection and also received VRC01 within 8 weeks before or after acquiring HIV in HVTN 703/HPTN 081 will have more limited viral reservoirs, before and after ATI, than those who initiated ART early in HIV infection and received placebo within 8 weeks of acquiring HIV in HVTN 703/HPTN 081.

3.2 Objectives and endpoints

3.2.1 Primary objectives and endpoints

Primary objective 1

- To evaluate the effect of early ART initiation, with or without having received VRC01 in the immediate pre-HIV acquisition period and/or during early

infection on the time to meeting ART re-initiation criteria in participants undergoing ATI

Primary endpoint 1

- Time to meeting criteria for ART re-initiation
- Frequency of sustained post-treatment HIV control, defined as ≥ 24 weeks off ART without meeting ART re-initiation criteria

Primary objective 2

- To evaluate the safety of ATI among HVTN 805/HPTN 093 participants

Primary endpoint 2

- Laboratory measures of safety, adverse events (AEs), SAEs, and rates of discontinuation

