The characteristics of the VISCONTI cohort and participants with delayed time to rebound give some hints into the potential mechanisms underlying virus suppression post-ATI and why it is more frequent with early ART. In general, early ART initiators have smaller, less diverse, and less transcriptionally active reservoirs. Further, their immune systems are believed to be better preserved and less exhausted. A recent sub-study of the SPARTAC trial has borne out some of these hypotheses.

The SPARTAC trial, which evaluated the impact of immediate vs delayed ART initiation after HIV diagnosis in both European and African participants, reported a 14% rate of post-treatment control at 1 year (16). Initial analyses suggested that smaller reservoirs were associated with PTC, as levels of total HIV-1 DNA prior to ART initiation and at ATI were associated with time to rebound. More recently, an in-depth analysis of the immunologic characteristics of the European (Subtype B virus-infected) SPARTAC PTCs has shown that measures of T-cell exhaustion (PD-1, Lag-3, and TIM-3) prior to ART initiation are strongly correlated with both levels of total HIV-1 DNA and time to rebound (26). Notably, no biomarkers at the time of ATI were identified that correlated with time to rebound. These results confirm the importance of smaller reservoirs and functional immune systems in post-treatment control, but do not elucidate a simple mechanism nor shed light on testing that can be done on ART-suppressed individuals to better predict their response to ATI.

Post-treatment control has continued to be reported in clinical trials and observational cohorts. Like the increased frequency of delayed rebound seen in African women in the PROMISE study, durable post-treatment control may be more common among African women. A recent SPARTAC sub-study revealed that the African SPARTAC cohort, all females infected with non-B (primarily C) subtypes, was more likely than the non-African SPARTAC cohort to maintain virologic control at study end (HR 3.9, 95% CI 1.75-8.81, $p < 0.001$) (1, 17). Further, 5 of 22 (23%) maintained VL <400 copies for the duration of follow up (median 4.48 years), while none of the non-African men maintained VL < 400 for

this duration. Of note, this frequency of post-treatment control is greater than any others included in the Martin et al analysis shown above in [Figure 2-3](#).

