3.3 ATI

For all participants, ATI begins with cessation of ART in Schedule 1, *Monitoring ATI*. Participants on ATI (ie, Schedule 1 or 2) who do not meet criteria for moving to the next visit schedule (ie, viral rebound or re-initiating ART) should continue on their current ATI visit schedule, including extended visits (as appropriate) until such time as they move to the next visit schedule or are terminated from the study. Schedule 1 and Schedule 2 extended visits occur quarterly and are designated as Visits Type A and Type B, with procedures specified for each visit type, in the laboratory and clinical procedures tables (see [Appendix E](#), [Appendix F](#), [Appendix H](#), [Appendix I](#), and [Appendix K](#)). For participants who meet criteria for reinitiating ART but decline to do so, see [Section 3.3.4](#).

3.3.1 Transition from Schedule 1, *Monitoring ATI* to Schedule 2, *ATI monitoring with viremia*

For participants on Schedule 1, *Monitoring ATI*, the following virologic criterion will trigger a transition to Schedule 2, *ATI monitoring with viremia*:

- Confirmed VL ≥ 200 copies/mL (ie, on 2 consecutive samples).

A confirmatory sample should be drawn at the next visit (within approximately 1-2 weeks) following the first VL result ≥ 200 copies/mL (see HVTN 805/HPTN 093 SSP for details).

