3.3.2 Transition from Schedule 1, *Monitoring ATI* to Schedule 3, *Follow-up on ART*

For participants on Schedule 1, *Monitoring ATI*, any of the following non-virologic criteria will trigger ART re-initiation and transition to Schedule 3, *Follow-up on ART*:

- Confirmed CD4+ T-cell count < 350 cells/mm³ (ie, on 2 consecutive samples)
- Any HIV-related syndrome (eg, ARS, an opportunistic infection)
- Pregnancy or breastfeeding
- ART re-initiation requested by participant
- ART re-initiation requested by primary HIV care provider or clinical research site (CRS) Investigator of Record (IoR) (eg, if deemed medically necessary)

A confirmatory sample should be drawn at the next visit (within approximately 1-2 weeks) following the first CD4+ T-cell count < 350 cells/mm³ (see HVTN 805/HPTN 093 SSP for details).

3.3.3 Transition from Schedule 2, *ATI monitoring with viremia*, to Schedule 3, *Follow-up on ART*

For participants on Schedule 2, *Monitoring ATI with viremia*, the following virologic criteria will trigger ART re-initiation and transition to Schedule 3, *Follow-up on ART*.

From the Week 0 visit to the Week 24 visit in Schedule 2:

- Viral load remains $\geq 1,000$ copies/mL for ≥ 4 consecutive weeks AND viral load has not dropped 0.5 log from the previous week

This ART re-initiation criterion applies irrespective of missed visits and must take account of VL results $\geq 1,000$ copies/mL experienced by a participant while on Schedule 1. Furthermore, assessing whether participants meet this criterion may require additional visits beyond those scheduled from Week 8 (Visit 48) to Week 24 (Visit 56) in Schedule 2. Ideally, these additional visits will be conducted weekly. These additional visits will be treated as interim visits (for more details, see the HVTN 805/HPTN 093 SSP).

After the Week 24 visit in Schedule 2, the ART re-initiation criterion is:

- Confirmed viral load ≥ 200 copies/mL (ie, on 2 consecutive samples).

A confirmatory sample should be drawn at the next visit (within approximately 1-2 weeks) following the first VL result ≥ 200 copies/mL (see HVTN 805/HPTN 093 SSP for details).

The above virologic ART re-initiation criteria are shown schematically in [Figure 3-1](#).

Figure 3-1 Virologic criteria for transition from Schedule 2 to Schedule 3 (ie, ART re-initiation)

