In addition, at any time during Schedule 2, any of the following non-virologic criteria will trigger prompt ART re-initiation and transition to Schedule 3, *Follow-up on ART*:

- Confirmed CD4+ T-cell count < 350 cells/mm³ (ie, on 2 consecutive samples)
- Any HIV-related syndrome (eg, ARS, an opportunistic infection)
- Pregnancy or breastfeeding
- ART re-initiation requested by participant
- ART re-initiation requested by primary HIV care provider or CRS IoR (eg, if deemed medically necessary).

A confirmatory sample should be drawn at the next visit (within approximately 1-2 weeks) following the first CD4+ T-cell count < 350 cells/mm³ (see HVTN 805/HPTN 093 SSP for details).

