4.1.1 Power to evaluate time to ART re-initiation criteria

Using data from the placebo arm of a therapeutic vaccine study which enrolled early treated patients (21), we modeled the time T (in weeks) to meet re-initiation criteria as a Weibull distribution with survival function $P(T > t) = \exp[-(\lambda t)^p]$, where $\lambda = \exp(-2.932) = 0.053$ and $p = 2.014$. From these parameters, we estimated the median time to meet re-initiation criteria as 15.6 weeks in the AMP placebo recipients. We can express the treatment effect in terms of either the HR θ or the factor β by which treatment increases the median time to meet re-initiation criteria; β and θ are related by $\beta = \theta^{1/p}$.

We model censoring of time to restart criteria using an exponential model and a maximum follow-up time of 72 weeks, where follow-up is censored at a rate of 20% per year due to either study termination or re-initiation of ART before reaching the restart criteria. Power for a 40%, 50%, 60%, and 70% reduction in hazard under different prevention efficacy scenarios are shown in [Table 4-1](#). These hazard reductions correspond to 29%, 41%, 58%, and 82% increases in the median time to meet restart criteria. Therefore, if VRC01 increases the median time to restart criteria 58% and the enrollment rate is 50%, then under the parent

study null hypothesis power to detect a difference in time to restart criteria is 72% while under the alternative hypothesis power is 62%.

Table 4-1 Power under different prevention efficacy results, different enrollment rates and different treatment effects, expressed as either reduction in hazard or percent increase in median time to meet re-initiation criteria

Enrollment Rate		Null hypothesis			Alternative hypothesis			
		25%	50%	75%	25%	50%	75%	
Expected number of placebos		7	13	20	9	18	26	
Expected number of VRC01		14	27	41	7	14	21	
Reduction in hazard	% Increase in median time to meet re-initiation criteria							
	40%	29%	20%	31%	44%	16%	27%	36%
	50%	41%	31%	49%	67%	23%	42%	57%
	60%	58%	46%	72%	89%	35%	62%	81%
	70%	82%	65%	90%	98%	52%	85%	95%

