4.2.3.1 Time to ART re-initiation criteria

The primary outcome is the time from the start of treatment interruption until the participant meets criteria to re-initiate ART.

For a comparison of the placebo group to historical controls a Cox proportional hazards model with the indicator of AMP placebo group versus historical control group will be used to estimate the cumulative incidence in each group, as well as the HR, all with 95% confidence intervals and associated 2-sided p-values, where the model controls for baseline covariates thought to potentially predict both HIV-1 infection and the instantaneous hazard of meeting the ART re-initiation criteria. This is needed for controlling for potential selection bias given that analyzed treatment groups are not randomized. Plots of the estimated cumulative incidence will be shown by treatment group.

A Cox proportional hazards model with the indicator of assignment to a mAb group versus the control group will be used to estimate the cumulative incidence in each of the infected VRC01 and infected placebo groups, as well as the HR, all with 95% confidence intervals and associated 2-sided p-values, where the model controls for baseline covariates thought to potentially predict both HIV-1 infection and the instantaneous hazard of meeting the ART re-initiation criteria. This is needed for controlling for potential postrandomization selection bias given that analyzed treatment groups are selected postrandomization. Plots of the estimated cumulative incidence will be shown by treatment group.

As a supportive analysis of this hypothesis, TMLE may be used to estimate cumulative incidences of the primary efficacy endpoint over time for the pooled mAb arm and the control arm. Iterative mean-based TMLE is used for this analysis as described by Benkeser et al (115). The Super Learner (116) is used to generate initial estimates of the conditional censoring distribution and the iterated conditional means. This analysis will use TMLE as implemented in the R package `survtmle` available on CRAN (117).

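### As written, restarting ART only for pregnancy or on request, without viral rebound, is a primary event and, before week 24, a failure of HIV control; the power model assumes otherwise and no event rule is given for the historical controls

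*Protocol*

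**What the plan says.** Protocol 3.2.1 gives two virologic primary endpoints: time to meeting the criteria for ART re-initiation, and "Frequency of sustained post-treatment HIV control, defined as ≥ 24 weeks off ART without meeting ART re-initiation criteria". Section 4.2.3.1 defines the time as "time from the start of treatment interruption until the participant meets criteria to re-initiate ART". Section 4.2.3.2 uses the same covariate-adjusted model to compare failure to maintain HIV control at 24 weeks, both between the two AMP arms and between AMP placebo and the historical controls. SAP sections 4 and 6.3 repeat this.

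Two places fix what the criteria are. Inclusion criterion 5 (5.1) points to Section 3.3 as a whole, and Section 6.3 points to 3.3.2 and 3.3.3. For Schedule 1, section 3.3.2 lists confirmed low CD4 count, HIV-related syndrome, pregnancy or breastfeeding, "ART re-initiation requested by participant", and a request by the care provider or investigator. Section 3.3.3 repeats the list for Schedule 2: "at any time during Schedule 2, any of the following non-virologic criteria will trigger prompt ART re-initiation".

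The first primary hypothesis is that participants will "suppress plasma viremia and maintain CD4+ T-cell counts longer during ATI than historical cohorts". The power model in 4.1.1 (and SAP 8) assumes that "follow-up is censored at a rate of 20% per year due to either study termination or re-initiation of ART before reaching the restart criteria". For the historical African cohort, section 2.2.2 describes control by viral load: "5 of 22 (23%) maintained VL <400 copies for the duration of follow up".

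**The concern.** A Schedule 1 participant has, by construction, no confirmed viral load of 200 copies/mL or more. If she becomes pregnant in week 10 and restarts ART, the endpoint text scores her as having met the criteria and as having failed to control HIV, although nothing virologic or immunologic has happened. The parent trial enrolled persons assigned female sex at birth, so the case is realistic.

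Three things are at stake. First, restarts unrelated to viral control enter the primary event count and the 24-week rate, and dilute a comparison meant to measure control. Second, the stated power belongs to a somewhat different endpoint from the one defined. Third, if the broad rule is applied to AMP participants and a viral-load rule to the historical cohorts, the extra events fall on one side only and work against the first primary hypothesis. The same event also feeds the immune-response and reservoir association analyses (4.2.4.2) and the safety team's review of the first 20 participants (11.1.1).

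**Working it through.** **Do the texts conflict?** Endpoint (3.2.1, 4.2.3): event = any criterion in Section 3.3. Section 3.3: pregnancy/breastfeeding and requests are criteria. Power text (4.1.1): restarts before the criteria are censored. Since pregnancy and requests are themselves criteria, almost the only restart left to censor is ART taken with no criterion met. The event definition and the power model therefore do not match. Neither document assigns event, censored or competing status to individual criteria; SAP 10.1 only tabulates the reasons.

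**Inputs.** Protocol 4.1.1: placebo survival S(t) = exp[−(λt)^p], λ = exp(−2.932) = 0.0533, p = 2.014; 72-week limit; loss 20% per year. SAP 8: log-rank test, alpha 0.05 (two-sided assumed). Protocol 4.1: 13 placebo + 27 VRC01, or 18 + 14, at 50% enrolment. Effect: hazard ratio (HR) 0.40.

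**The plan's own figures.** Median = (ln 2)^(1/p)/λ = 0.8336/0.0533 = 15.6 weeks, as stated. Simulated power with all loss censored (hazard −ln 0.8 = 0.223 per year): 72% (13+27) and 63% (18+14), against 72% and 62% stated. The plan's power is right for a model that censors.

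**Counting the restarts.** The documents do not split the 20%, so the share is an assumption: half or all of it, equal in both arms, total exit rate unchanged. *All* is an upper bound, because 4.1.1 also names study termination.

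| Arms | Censored | Half counted | All counted |
|---|---|---|---|
| 13+27 | 72% | 69% | 67% |
| 18+14 | 63% | 61% | 59% |

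With 13+27, such restarts make up 1.9 of 38 events (half) or 3.7 of 40 (all). The SAP's arm sizes (13+28, 15+15) also lose about 2 to 5 points.

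**24-week control.** S(24) = exp[−(0.0533 × 24)^2.014] = 19.4% for placebo; with HR 0.40, 0.194^0.4 = 51.9%. Counting restarts as failures multiplies both by 0.8^(share × 24/52):
- half: × 0.950 gives 18.4% and 49.3%
- all: × 0.902 gives 17.5% and 46.8%

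**Pregnancy-only restarts**, assumed at 2% or 5% per year and counted as events: power 71–72% or 71% (13+27), and 63% or 62% (18+14). The cost is about 1 point or less.

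**Requests are different.** Suppose 10% or 20% of participants ask to restart 0–4 weeks before they would have met another criterion. Counting the requests leaves power at 71–72% and 62–63%. Censoring them lowers it to 68% or 63% (13+27) and 59% or 55% (18+14).

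**The case against.** An all-criteria composite is a legitimate endpoint, and objective, endpoint and analysis all use the same term. This stands, and for requests the check favours the written rule: a request may follow viremia, so censoring it could be informative. It does not rescue calling a pregnancy-only restart a failure of HIV control, nor the mismatch with the power text.

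Purely virologic readouts exist (time to viral load of 200, table of restart reasons), contraception is required, the study is exploratory, and this SAP is mainly for safety reporting. These limit misreading and keep the numbers small. They do not define the primary event, and the SAP repeats the virologic endpoint text.

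Three stronger readings are tempting and not supported:
- *Sections 5.3 and 6.7.1 contradict each other on pregnancy.* They do not. Section 5.3 refers to 6.7.1, which terminates switch-phase cases and keeps ATI-phase cases on Schedule 3. A switch-phase pregnancy precedes Day 0 and never enters the endpoint.
- *The 24-week definition leaves an early non-virologic restart undefined.* Such a participant fails both parts: she is not 24 weeks off ART, and she has met a criterion.
- *The loss against historical controls can be quantified.* The documents give a group size only for the African cohort and no assumed hazard ratio for that comparison. The placebo Weibull leaves 0.04% event-free at 52 weeks, while 2.2.2 reports 14% post-treatment control at 1 year in that trial.

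**Conclusion.** The point holds and should be fixed, with medium confidence. As written, the primary event and the 24-week control rate include restarts that say nothing about viral or CD4 control, and the power model rests on a different rule. Between the AMP arms the effect is modest: roughly 2 to 5 power points and a 5–10% relative reduction in modelled 24-week control if half to all of the 20% yearly loss were such restarts, and about 1 point or less for pregnancy alone at 2–5% a year. These sizes rest on assumed rates, equal in both arms, and on the plan's Weibull model.

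For the historical comparison only the direction can be stated: counting such restarts in AMP participants alone biases against the first primary hypothesis. Its size cannot be estimated from the documents. A reader might infer that every non-virologic criterion should be censored. The documents do not support that: confirmed CD4 decline is part of the hypothesis, and requests may follow viremia.

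**What to change.** Change the analysis text only (protocol 3.2.1, 4.1.1 and 4.2.3, and the SAP). The clinical restart rules stay as they are.

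- (a) Virologic, confirmed CD4 and HIV-related-syndrome criteria are events.
- (b) A restart solely for pregnancy or breastfeeding, before any other criterion is met, is a competing event (censored for the hazard ratio) and not a failure of HIV control. A sensitivity analysis counts as events those with confirmed viral load of 200 copies/mL or more.
- (c) Participant and provider or investigator requests stay events in the primary analysis. A sensitivity analysis treats them as a competing event, split by Schedule 1 and Schedule 2.
- (d) Apply the same event rule to the historical controls as far as their data allow, and state any mismatch.
- (e) Align the censoring sentence in protocol 4.1.1 and SAP 8 with these classes. State how a provider request that leads to both restart (3.3.2, 3.3.3) and early termination (5.3) is coded.

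The cost is wording plus one or two sensitivity analyses. AMP participants need no new data, because restart reasons are already tabulated (SAP 10.1); historical data may support only part of the rule. The change assumes that pregnancy restarts are non-informative. SAP 7 describes the parent trial's unblinding in the past tense, so date the change and state that it was made without reference to outcomes by arm.
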